Secondary Aims: We will also explore potential within- and between-subject effects of Enhanced HBST versus standard HBST on positive/negative affect, social support, sex risk behavior, and health empowerment.

Overview of the research: During a “start-up” period of 6 months, we will use qualitative methods (focus group [$N=8$], individual interviews [$N=10$]) to inform ongoing consultation with Devicix (an electrical and software engineering firm) on refining a mobile technology for monitoring HBST use, ultimately preparing it for deployment. Then, during the “study phase,” 40 high-risk MSM in the Providence, RI area will be randomly assigned to one of two conditions: An “enhanced” HBST condition ($N=20$) or standard HBST ($N=20$). In both conditions, 3 HBST kits will be sent by mail at 3-month intervals over the course of 6 months (baseline, 3-months, 6-months). We chose to deliver HBSTs by mail given recent evidence that a majority of MSM prefer this method of receiving kits (as opposed to pharmacy pickup or vending machines)^{50,51}. In the “enhanced” HBST condition, mailed test enclosures will be equipped with a mobile monitoring sensor (see Section 3C.3.1.) that triggers an alarm on dedicated mobile phones carried by qualified HIV test counselors (QHTC). QHTCs will then conduct a follow-up call to the user within 24 hours. In the HBST alone condition, test kits will simply be mailed to participants with contact information for local HIV care, confirmatory testing, STI testing, and PrEP. All participants will be oriented to the study during a baseline, in-person appointment at Brown University. Then, participants will complete monthly assessments online over the course of 7 months while on the study (see Fig. 1 for a timeline). To complete the project within the 2-year period, 4 participants per month will be recruited on a rolling basis (beginning in month 6 of year 1), allowing all participants to finish the study by month 10 in Year 2.

C.2 Participant Population

The research has three phases: (1) Focus group phase [$N = 8$], (2) individual interview phase [$N = 10$], and (3) pilot study phase [$N = 40$]. *All* participants (regardless of which phase they are participating in) will meet the same criteria.

Inclusion criteria are as follows:

1. Biologically male
2. Aged 18 or older

3. Have not been tested for HIV in the last year

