4. Report unprotected anal sex (or anal sex without a condom or having taken PrEP that day) with a casual male partner at least once in the past 6 months
5. Sex with a partner met online in the past year
6. Stable residence
7. Use of an Android smartphone with service contract and data plan
8. Fluent in English

Exclusion criteria:

1. Individuals who are HIV-positive
2. Individuals who participated in other phases of the research
3. Individuals who report being coerced to participate

C.3 Recruitment Procedures

We will recruit participants using ads in social networking mobile apps and websites that gay men often use to meet partners (e.g., Grindr, Jack'd, Adam4Adam). App users who click on an ad will be directed to a webpage that provides more information on the study. If they are interested in participating, a link to an online screening survey will be made available at the bottom of the page. Participants will provide their informed consent prior to answering questions on the screen. The screening questionnaire will be collected using Qualtrics® survey software. Screening items will only address eligibility criteria (see Appendix B, Section I.). Participants determined to be eligible based on this brief screening will be contacted by email and phone to provide more information about the study. Participants who are interested in participating in the full study will then schedule an appointment to come to the research offices at Brown.

C.4 Design and Methods

Phase I: Start-Up and Qualitative Research

Focus groups. At the start of the project period, we will conduct a focus group with 8 participants from the target group in which we will present the proposed monitoring and follow-up system, and solicit participant feedback. Key questions to be addressed include the desirability of “active” follow-up after HBST, when and how participants would like to receive follow-up, and what users would like follow-up calls to address. \$50 will be paid to focus group participants.

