Experimental conditions. In this 7-month longitudinal study, 40 participants will be randomized to receive either “enhanced” HBST ($N=20$) or standard HBST ($N=20$). All will have 3 OraSure® test kits shipped to their homes 1-week after baseline, 3-months, and 6-months. Those in the “enhanced” HBST condition will receive follow-up calls within 24 hours after opening their tests. Those in standard HBST will be provided contact information for local services in their test kits, in addition to the information provided by OraSure®.

Measures. Demographics, past HIV testing history, sexual behavior, and other relevant variables will be collected at baseline. Throughout the 7-month study period, participants will complete online assessments each month inquiring about whether they used a study-provided HBST kits in the last month and what the result was. Items will also assess whether they were provided referral to a local agency for additional prevention services (e.g., additional HIV testing, STI testing, PrEP consultation, HIV risk reduction counseling) by a professional in the last month, and whether they sought each service over the last month. Participants will also complete Timeline Follow Back (TLFB^{55,56}) assessments of their sexual behavior over the past month. The TLFB has proven to be one of the more reliable and valid assessments available for sexual behaviors⁵⁷⁻⁶⁴, and recent evidence suggests that optimal accuracy in reporting may be achieved with short follow-up periods (e.g., 30 days)⁵². Monthly online assessments will also measure general positive/negative affect over that time using the positive and negative affect scales of the PANAS-X⁶⁵, a 20-item scale that asks participants to rate various emotion words according to the extent they have “felt this way over the past month,” on a 1 (*very slightly*) to 5 (*extremely*) scale. These subscales have excellent psychometric properties when used to measure trait affect⁶⁵. Health empowerment will be measured each month using the Patient Activation Measure (PAM-13⁶⁶), and social support will be assessed with 3 subscales of the Received Support Scale (Emotional, Informational, Satisfaction). Both measures have excellent psychometric properties⁶⁶⁻⁶⁹.

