
Figure 3. Timeline of study assessments

perceptions of “enhanced” HBST or HBST alone, additional procedures/services they might have preferred. Those in the “enhanced” condition will be asked about their impressions of counseling over the phone and the usability of the monitoring method. Participants will be paid \$20 for completing the baseline in-person appointment and \$15 per monthly assessment (\$105 total), with a \$55 bonus for completing all assessments on time (within +/- 5 days of being assigned).

Planned Analyses/Power Considerations. As this is a preliminary study, the primary goal is to explore evidence for the feasibility, acceptability, and utility of “active” monitoring and follow-up with HBST, as well as its effects on testing likelihood and frequency compared with usual HBST. As such, data analysis will be primarily descriptive. To address Aim 1, we will explore the number of successful phone contacts with those in the “enhanced” HBST condition, whether contacts involved counseling and/or referral, and qualitative data/ratings of acceptability, feasibility, and preferences. To address Aim 2a, we will compare the overall number of participants reporting any HBST use and the mean number of tests used across the conditions over the study period. To address Aim 2b/c, we will also compare the number of participants receiving HIV test counseling, referral for additional prevention services, and the number who successfully followed-up with these services. Finally, to address the secondary aims, we will compare mean frequencies of unprotected anal sex (condomless or without having taken PrEP that day) and mean levels of positive/negative affect, health empowerment, and social support by condition and testing status. We are aware of the limitations of relying on small scale studies for generating broad conclusions about the efficacy and/or effect sizes of interventions⁹⁶. As such, we are primarily interested in examining the pattern of results, rather than definitively testing hypotheses. We believe a sample size of 40 should allow some exploration of the direction of effects, while remaining within the scope of an exploratory project.

C.5. Human Subjects Involvement, Characteristics, and Design

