Participants will be 40 males who are 18 years of age or older, who report having sex with a partner met online in the past year, and who have not received an HIV test in the last year. Focusing recruitment toward these individuals will allow us to examine whether remote monitoring and follow-up after HBST are helpful specifically among those who rarely test and may be “hard to reach” with more traditional HIV prevention services. Eligible participants will also report having had unprotected anal sex (anal sex without a condom or having taken PrEP that day) with a casual male partner at least once in the last 6 months. This criterion will ensure that the research is conducted among MSM who are at high risk for HIV. Since the research involves receiving HBST kits by mail, eligible participants will also be required to have a secure and stable residence to minimize the potential that tests may be stolen or diverted. This criteria was informed by past qualitative studies suggesting that most high-risk MSM prefer to receive tests by mail^{50, 51}, as opposed to other delivery avenues (e.g., vending machine, pharmacy pickup). However, future research should address methods for providing “active” follow-up after HBSTs that are delivered via these routes, since many at highest risk may not have stable residences. Next, to be eligible, participants must currently have an Android smartphone with a data plan. If successful, we hope to extend this technology to iPhone users, since they constitute a large share of the overall smartphone market. However, acquiring approval for iPhone-compatible software is an extensive process that often takes months. The Android platform is open source, allowing flexibility in deployment, so the current study will focus on Android users.

Finally, eligible participants will also be required to be fluent in English. While many of the study's materials could be easily translated into Spanish (or other languages), hiring bilingual or Spanish-speaking QHTCs that are able to conduct follow-ups would be prohibitive for a study of this scope. No special or vulnerable populations, as defined by 45 CFR Part 46 (e.g., prisoners, pregnant women, fetuses) are involved.

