Participants will be recruited from the community using ads in popular gay social networking mobile apps (e.g., Grindr, Jackd, Scruff). Participants expressing interest in the study will be screened online. Those meeting eligibility criteria will be contacted by phone and email to schedule an in-person appointment to begin the study. Next, participants will complete baseline measures online. Then, participants will be randomized to a condition. For those in the "enhanced" condition, RAs will inform participants about the study's purpose and guide them in downloading study software onto their smartphones. Although participants will not need to actively provide any input through the app, RAs will instruct participants to keep the app installed, their Bluetooth sensor enabled, and their phones near them throughout the 7-month study. RAs will also ask participants to notify them as soon as possible if they lose their phone or get a new one, their data is erased, or if their service plan changes. Next, RAs will inform all participants that they should expect to receive an email each month with a unique link, and that clicking this link will allow them to complete their monthly assessments. They will also be informed that HBST kits will be mailed to them 1 week after their appointment, and then again in 3 months and 6 months, which they can choose to take or not. However, should they choose to do so, those in the "enhanced" condition will be told that they should expect a call from a QHTC associated with the study within 24 hours after opening their test, and that these calls are intended to provide counseling and referrals after taking the test (which participants can refuse). Finally, participants will be asked to complete a 30-minute follow-up interview about the study via phone after completing the study. They will be informed that they can pick up payments for completing study assessments at the research offices anytime during or after the study.

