STUDY PROTOCOL

Title: Exploring Use of a Real-time, Remote Monitoring and Follow-up System for Home-based, HIV Self-testing Among High-risk Men Who Have Sex With Men (MSM)

NCT#: NCT02876926

Date of document: Last reviewed and approved by Brown IRB on 9/15/18

Analysis plan. Monthly survey responses were first aggregated across the entire study period for each of the study's key outcomes: HIV testing rates, STI testing rates, receipt of risk reduction counseling, receiving prevention supplies, PrEP referrals, and being prescribed PrEP. Linear or Poisson regression models with planned contrasts were then used to explore differences in these outcomes between the study groups across the entire 7-month study period. Next, we used survey completion dates to examine rates of each outcome across the 3-month study intervals (baseline, 3-months, and 6-months), which align with current CDC recommendations for HIV testing every 3-6 months among high-risk MSM. Repeat testing was defined as having tested at least twice in at least two of these intervals over the course of the study period. To explore the effect of condition outcomes over time, we used generalized estimating equations (GEE) with binomial distributions and logit-link functions for binary outcomes, and Poisson distributions and with log-link functions for count outcomes. All models were analyzed using an intent-to-treat (ITT) approach that involved retaining participants who withdrew from the study and assuming that they did not engage in any key outcome. Significance was defined as p -values ≤ 0.05 . All analyses were conducted in Stata 14.

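### As worded, the secondary sexual-risk outcome counts acts missing either a condom or PrEP, including condom-protected acts by men not on PrEP; the eligibility text most naturally means acts missing both

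*Protocol*

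**What the plan says.** Protocol C.1 (Secondary Aims) states the aim as "We will also explore potential within- and between-subject effects of Enhanced HBST versus standard HBST", with sexual risk behaviour among the measures listed. C.4 (Planned Analyses/Power Considerations) then gives the outcome: "we will compare mean frequencies of unprotected anal sex (condomless or without having taken PrEP that day".

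The same term appears twice as an entry criterion. C.2, inclusion criterion 4, has "unprotected anal sex (or anal sex without a condom or having taken PrEP that day". C.5 has "unprotected anal sex (anal sex without a condom or having taken PrEP that day".

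On data, C.4 (Phase II, Measures) collects sexual behaviour every month by Timeline Follow Back (TLFB) with a one-month window. It gives no rule for classifying an act by condom and PrEP status. It also says "Demographics, past HIV testing history, sexual behavior, and other relevant variables will be collected at baseline", and C.5 places this before allocation: "Next, participants will complete baseline measures online. Then, participants will be randomized to a condition". No use of the baseline value in the comparison by condition is stated.

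The SAP (Analysis plan) lists its key outcomes as "HIV testing rates, STI testing rates, receipt of risk reduction counseling, receiving prevention supplies, PrEP referrals, and being prescribed PrEP". Sexual behaviour is not among them. The SAP is written in the past tense and ends "All analyses were conducted in Stata 14".

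**The concern.** The C.4 gloss joins two failures of protection with *or*. An analyst who codes from that sentence would count a condom-protected act by a man who took no PrEP, and also a condomless act on a PrEP day. The eligibility wording puts both protections under a single *without*, which most naturally excludes both kinds of act. One term therefore carries two different rules, one for entry and one for the outcome.

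What is at stake is whether the measure can respond. C.5 says the follow-up calls offer referral for PrEP and for risk-reduction counselling, so changes in PrEP or condom use are what this outcome ought to register. Coded as written, it would barely move when men not on PrEP take up condoms, or when men who do not use condoms take up PrEP. A reader of a reported mean could not tell which acts it contained.

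**Working it through.** The plan gives no rate, SD or power figure for this outcome, so there is no stated number to reproduce. The check is a reading of the texts, followed by an illustration on assumed inputs.

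**1. The two wordings side by side**

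| Act | C.4 as written (no condom *or* no PrEP) | C.2 and C.5, natural reading (neither) |
|---|---|---|
| No condom, no PrEP | counted | counted |
| Condom, no PrEP | counted | not counted |
| No condom, PrEP that day | counted | not counted |
| Condom and PrEP that day | not counted | not counted |

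Without any assumption, the literal count minus the neither count equals the number of acts with exactly one protection.

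**2. Levels, on assumed inputs.** Take a = 8 acts, c = share with a condom, q = share on PrEP days, with c and q independent. Then literal = a(1 − cq), neither = a(1 − c)(1 − q), and the difference = a[c(1 − q) + (1 − c)q]. Each cell shows literal / neither, then the share of literally counted acts that had one protection.

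| q | c = 0.25 | c = 0.50 | c = 0.75 |
|---|---|---|---|
| 0 | 8 / 6 (25%) | 8 / 4 (50%) | 8 / 2 (75%) |
| 0.1 | 7.8 / 5.4 (31%) | 7.6 / 3.6 (53%) | 7.4 / 1.8 (76%) |
| 0.3 | 7.4 / 4.2 (43%) | 6.8 / 2.8 (59%) | 6.2 / 1.4 (77%) |

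**3. Response to a change or an arm difference, on assumed inputs.** The literal share of acts, 1 − cq, changes with c at rate −q and with q at rate −c. The neither share, (1 − c)(1 − q), changes at rates −(1 − q) and −(1 − c).

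- Condom share 0.4 to 0.6 at q = 0.05: literal 0.98 to 0.97, a fall of 0.01; neither 0.57 to 0.38, a fall of 0.19.
- PrEP share 0.05 to 0.25 at c = 0.4: literal 0.98 to 0.90, a fall of 0.08; neither 0.57 to 0.45, a fall of 0.12.
- At q = 0 the literal share is 1 whatever the condom use. At c = 0 it is 1 whatever the PrEP use.

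**4. Use of baseline, 20 per arm, in SD units.** Unadjusted SE = √(2/20) = 0.316, so the 95% half-width is 2.024 × 0.316 = 0.640, using t on 38 df. The adjusted half-width is 2.026 × E[√(2/20 + d²/Sxx)] × √(1 − r²), using t on 37 df. Here r is the assumed baseline correlation, d the chance baseline difference between arms and Sxx the within-arm baseline sum of squares; the expectation was taken over 20,000 simulated randomisations.

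| r | 0 | 0.3 | 0.5 | 0.7 |
|---|---|---|---|---|
| Half-width | 0.650 | 0.620 | 0.562 | 0.464 |

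The adjusted and unadjusted widths are equal at r = 0.169 (unrounded inputs). Below about 0.17, adjustment slightly widens the interval. These are linear-model approximations; the documents give no distribution for act counts.

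**The case against.** The strongest reply is that the intent is plain. The C.4 parenthesis explains the noun *unprotected*, and a condom-protected act is not unprotected. The two eligibility passages support the neither reading, and C.5 ties the term to high HIV risk. This largely stands: the C.4 wording is probably loose drafting. It does not close the point, because C.2 and C.5 define entry, no supplied text says they govern the outcome, and C.4 is the only place where the outcome is defined.

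Second, every magnitude above is assumed. That also stands. In the q = 0 row the percentages simply return the condom shares put in. The grid says nothing about this trial; it shows only how the two rules diverge.

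Third, comparing raw means suits a descriptive pilot, and the gain from adjustment is conditional. At r = 0.3 the half-width moves only from 0.64 to 0.62 SD. TLFB is described only for the monthly assessments, so a comparable baseline measure may not exist. This stands too, so adjustment is offered as an option and its absence is not treated as a defect.

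Fourth, the neither rule can be applied to existing data only if the TLFB captured condom use and same-day PrEP by act or day, which the documents do not say. The fix is conditional on that.

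**Conclusion.** The point holds as a minor one. The only supplied definition of the sexual-risk outcome, followed literally, counts acts with one protection as unprotected. It differs from the natural reading of the same term in C.2 and C.5, and neither the Measures text nor the SAP resolves the difference. Coded that way, the measure would be nearly insensitive to condom uptake among men not on PrEP and to PrEP uptake among men not using condoms. The size of the effect in this trial is unknown.

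A reader might infer three stronger things that the documents do not support:

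- **That acts were in fact miscoded.** Nothing shows this, and a coding rule may exist in material not supplied, such as the funding proposal, Appendix B or the TLFB application.
- **That silence on the baseline value biases the comparison by condition.** It does not. Baseline is collected before randomisation, and leaving it out can cost only precision.
- **That the trial's main results are in doubt.** The primary aims and all SAP key outcomes, including PrEP referral and prescription, are untouched. This is one secondary measure among 40 participants in a study whose analysis is mainly descriptive.

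**What to change.** Reword the C.4 outcome so that an act counts only if no condom was used and no PrEP was taken that day, consistent with C.2 and C.5. Code the TLFB data to that rule, provided the TLFB records both items by act or by day. If coding is already done, as the SAP's past tense suggests it may be, report the rule that was used.

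Optionally, check whether the baseline sexual-behaviour measure and its recall window are comparable with the monthly TLFB. If they are, report a baseline-adjusted comparison by condition beside the planned means, labelled post hoc if the analyses are complete.

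The cost is one sentence of definition and one coding rule. The option adds a comparability check and one simple model, at the price of a slightly wider interval if the baseline correlation is below about 0.17. If the TLFB did not link condom and PrEP use by act or day, the rule cannot be applied to the existing data, and the report should say so.

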Procedure. See Figure 3 for study timeline. Interested participants will be screened online, and those eligible will be contacted by a research assistant (RA), who will schedule an in-person appointment to begin the study. At this appointment, participants will complete baseline measures and be oriented to the study. In the “enhanced” HBST condition, participants will be informed that sensors will accompany their HBST kits and to expect a call from study QHTCs within 24 hours after opening them, should they choose to test. Study software will then be downloaded onto the participant’s phone, and they will be instructed to keep their Bluetooth feature enabled at all times and to

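### Secondary outcomes are to be compared by condition and by testing status, but only condition is randomised: read the direction of effects from the arms and report testing-status contrasts separately as associations

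*Protocol*

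**What the plan says.** - **Aim.** Protocol C.1, Secondary Aims: "We will also explore potential within- and between-subject effects of Enhanced HBST versus standard HBST". The outcomes are affect, social support, sexual risk behaviour and health empowerment. Testing status is not mentioned.
- **Analysis.** Protocol C.4, Planned Analyses/Power Considerations, compares mean frequencies of unprotected anal sex and "mean levels of positive/negative affect, health empowerment, and social support by condition and testing status". It ranks neither grouping above the other, does not define testing status and names no covariate. On sample size it says: "We believe a sample size of 40 should allow some exploration of the direction of effects".
- **How testing status arises.** C.5 says of the mailed kits, "which they can choose to take or not". C.4, Procedure, tells enhanced-arm participants "to expect a call from study QHTCs within 24 hours after opening them, should they choose to test".
- **Testing as an outcome.** C.4: "To address Aim 2a, we will compare the overall number of participants reporting any HBST use", compared across the conditions.
- **Baseline data.** C.4, Measures: "Demographics, past HIV testing history, sexual behavior, and other relevant variables will be collected at baseline". C.5 gives the order: "Next, participants will complete baseline measures online. Then, participants will be randomized to a condition".
- **SAP.** The Analysis plan lists six key outcomes, on HIV and STI testing, counselling, supplies and PrEP. None of the secondary outcomes is among them. It compares study groups, with no testing-status term and no baseline covariate.

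**The concern.** Two contrasts of different standing share one sentence. The contrast by condition is protected by randomisation. The contrast by testing status is not: men who use a kit may already differ from those who do not in sexual risk, mood, activation or support. Testing status also arises after randomisation and is something the enhanced arm may change, so comparing arms within testers or within non-testers loses the protection of randomisation too.

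The pilot is meant to show direction and pattern, so the sign of a difference is what a reader will take away. An unlabelled tester versus non-tester difference could be taken for an effect of testing, or of the follow-up call that comes with it in the enhanced arm, when it only shows who tests.

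A separate, lesser matter is that sexual behaviour is recorded before randomisation but no plan is given to use it in the randomised comparison.

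**Working it through.** The sample size of 40 is not derived from any effect size, SD or power, so there is no figure to reproduce. The documents give no testing rate, correlation or SD. The inputs marked as assumed are illustrations.

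**1. Testers versus non-testers, no true effect**

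Inputs: N = 40, 20 per arm (protocol C.1 and C.4). Assumed: ever/never classification; share testing p = 0.6 or 0.8; outcome SD = 1; a normally distributed propensity to test with correlation ρ to the outcome.

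Expected gap = ρ × φ(z_p) / [p(1 − p)], where φ is the standard normal density and z_p the normal quantile of p.
- p = 0.6: gap = 1.610ρ; SE = √(1/24 + 1/16) = 0.323
- p = 0.8: gap = 1.750ρ; SE = √(1/32 + 1/8) = 0.395

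The sign shares come from 40,000 simulated trials of 20 + 20 per setting:

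| ρ | Gap, p = 0.6 | Sign follows selection | Gap, p = 0.8 | Sign follows selection |
|---|---|---|---|---|
| 0 | 0 | 50% | 0 | 50% |
| 0.1 | 0.16 | 69% | 0.17 | 67% |
| 0.2 | 0.32 | 84% | 0.35 | 81% |
| 0.3 | 0.48 | 94% | 0.52 | 91% |
| 0.5 | 0.80 | over 99% | 0.87 | 99% |

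The arm contrast in the same simulations was positive in 50% of trials throughout, as it should be with no effect.

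**2. Within-person monthly contrast**

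Assumed: kits in months 1, 4 and 7; 60% testing per kit; stable selection only; trait–outcome correlation 0.2 and 0.5. The sign followed selection in 50% of simulated trials, so stable differences cancel. Confounding that varies from month to month was not modelled and could remain.

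**3. Arm contrast within testing groups (only if the two factors are crossed)**

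Assumed: 80% testing in the enhanced arm, 60% in the standard arm, ρ = 0.1 to 0.5, no true effect. Enhanced minus standard:
- Testers (16 v 12): ρ(0.350 − 0.644) = −0.03 to −0.15 SD; SE √(1/16 + 1/12) = 0.38
- Non-testers (4 v 8): ρ(−1.400 + 0.966) = −0.04 to −0.22 SD; SE √(1/4 + 1/8) = 0.61

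This is below sampling error at this size, and zero under this model if the arms test equally.

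**4. Baseline adjustment of the randomised comparison**

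This removes no bias, because the arm contrast is already unbiased. For a continuous mean of seven monthly values ($105 / $15 = 7 assessments), with months correlating 0.5 with each other, the variance factor is (1 + 6 × 0.5)/7 = 0.571. A baseline measure correlating b with each month cuts the variance by b²/0.571:
- b = 0.1: 0.01/0.571 = 2%
- b = 0.2: 0.04/0.571 = 7%
- b = 0.3: 0.09/0.571 = 16%
- b = 0.5: 0.25/0.571 = 44%

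These figures do not carry over directly to a count of unprotected acts. The Timeline Follow Back is described only for the monthly assessments, so it is not documented that baseline sexual behaviour is measured the same way. The gain is therefore of unknown size.

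**The case against.** The strongest reply is that the plan contains no error. The secondary aim is worded as enhanced versus standard HBST, and the remark about direction follows a caution about effect sizes of interventions, so the arm contrast is the natural reading. The analysis is declared mainly descriptive, and means by testing status are legitimate description. The aim also mentions within-subject effects, and kit use is asked monthly, so a within-person contrast may be what is meant.

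Much of this stands. A reader might infer that the protocol claims a causal effect of testing; it makes no such claim. A reader might also infer that the testing-status contrast will nearly always point the wrong way. That needs an ever/never contrast and a correlation of at least about 0.2; at 0.1 the share is 67% to 69%, and at zero it is 50%. Nor do the documents support a large promised gain from baseline adjustment: affect, empowerment and support are not named among the baseline measures, and sexual behaviour is analysed as a frequency.

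What remains is that the analysis paragraph gives the two groupings equal standing and leaves testing status undefined. The SAP does not settle this, because its key outcomes omit all the secondary ones.

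**Conclusion.** The point holds as a minor matter of specification and labelling. Only the comparison by condition is randomised and answers the secondary aim. Testing status is self-selected after randomisation and is itself an Aim 2a outcome, so differences between testers and non-testers are partly selection. How large that part is cannot be known from the documents. The range in the working depends on the assumed correlation, the assumed testing rate and the ever/never definition, and it vanishes if propensity to test is unrelated to the outcome. Baseline adjustment is a separate and optional gain in precision. The randomised comparison without it is valid. These are secondary aims of an exploratory pilot, so nothing in the main conclusions depends on this.

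**What to change.** 1. State that the direction of effects of enhanced HBST on the secondary outcomes is read from the arms as randomised. For unprotected anal sex, use a count model on the monthly values, adjusted for baseline sexual behaviour, and say that the adjustment is for precision.
2. Adjust affect, empowerment and support only for their own baseline values, and only if these were in fact measured at baseline.
3. Define testing status (ever/never, or month by month from the monthly kit-use item). Report contrasts by testing status in a separate table, together with any arm contrasts within testing groups, labelled as non-randomised associations and not as effects of testing or of condition.

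The cost is wording and a few models. Baseline sexual behaviour and monthly kit use are already collected. The SAP is written in the past tense, so any model added after results were seen should be labelled post hoc.
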